#### 4.2 Intervention

Road Map/Schema (1st CR/VGPR after conventional therapy): A cycle consists of treatment with 3F8 for 5 days. GM-CSF is started 5 days in advance of each 3F8 cycle. The break between end of a cycle of 3F8/GM-CSF and start of next cycle is approximately 2-to-4-weeks through 4 cycles; subsequent breaks are ~6-8 weeks. 13-*cis*-retinoic acid is started after cycle 2.

Cycle 1	high-dose 3F8* + GM-CSF
2-4 weeks off	
Cycle 2	high-dose 3F8* + GM-CSF
2-4 weeks off– 13- cis -retinoic acid x14 days on, x14 days off	
Cycle 3	3F8 + GM-CSF
2-4 weeks off– 13- cis -retinoic acid x14 days on, x14 days off	
Cycle 4	3F8 + GM-CSF
6-8 weeks off – 13- cis -retinoic acid x14 days on, x14 days off, x14 days on	
Cycle 5	3F8 + GM-CSF
6-8 weeks off – 13- cis -retinoic acid x14 days on, x14 days off, x14 days on	
Cycle 6	3F8 + GM-CSF

Continue with ~6-8-week breaks through 24 months from 1st dose of 3F8. The treatment schedule may require minor adjustment as clinically indicated (e.g., due to PDH closure for holidays). Patients can complete the missed day of 3F8 the following week, so they receive

Amended: 02/24/15

## Memorial Sloan-Kettering Cancer Center IRB Protocol

IRB#: 09-159A(10)

a full 5-day cycle. GM-CSF will be continued through the 3F8 make-up day at the 500 mcg/m^2 dose.

\*High-dose 3F8 will be administered only for patients enrolled on protocol from A(0) to A(7). Starting with A(8), patients receive standard dose (20mg/m^2/day) during cycles 1 and 2.

### 5.0 THERAPEUTIC/DIAGNOSTIC AGENTS

#### 5.1 3F8 monoclonal antibody (IND number of BB-IND-8449)

5.1.1 Source and Pharmacology: Monoclonal antibody 3F8 is purified by column chromatography. The final product is tested to assure that it is free of nucleic acid, murine viruses, bacteria, fungi, mycoplasma and pyrogens. Supplier: 3F8 is manufactured as an investigational agent.

5.1.2 Formulation and Stability: The purified antibody is frozen at -80°C, at 2 mg/mL 0.1 M citrate-phosphate pH 4.2 buffer in glass vials. At -80°C it is stable for at least 3 years. For iv administration, 3F8 should be diluted into 10 ml 5% human serum albumin and millipore (0.2 µm) filtered before use. Route of Administration: iv infusion.

5.2 Yeast-derived human recombinant granulocyte-macrophage colony stimulating factor GM-CSF; LEUKINE (sargramostim) is produced by Berlex Laboratories, Seattle, WA.

5.2.1 LEUKINE is a sterile, white, preservative-free, lyophilized powder suitable for iv infusion upon reconstitution of 250 mcg vials; these vials should be reconstituted aseptically with 1.0 ml Sterile Water for Injection, USP (without preservative). The reconstituted LEUKINE solutions are clear, colorless, isotonic with a pH of 7.4 ± 0.3, and contain 250 mcg/ml of Sargramostim. The single-use vial should not be re-entered or reused. Do not save any unused portion for later administration. Vials containing 500 mcg of LEUKINE are already in solution and are multiple dose vials.

5.2.2 During reconstitution the Sterile Water for Injection, USP should be directed at the side of the vial and the contents gently swirled to avoid foaming during dissolution. Avoid excessive or rigorous agitation; do not shake.

5.2.3 Dilution for iv infusion should be performed in 0.9% Sodium Chloride Injection, USP. If the final concentration of LEUKINE is below 10 mcg/ml, Albumin (Human), add 1 mg Albumin (Human) per 1 ml 0.9% Sodium Chloride Injection, USP (e.g. use 1 ml 5% Albumin [Human] in 50 ml 0.9% Sodium Chloride Injection, USP).

Amended: 02/24/15

## Memorial Sloan-Kettering Cancer Center IRB Protocol

IRB#: 09-159A(10)

5.2.4 An in-line membrane filter is not to be used for iv infusion of LEUKINE.

5.2.5 LEUKINE contains no antibacterial preservative and therefore should be administered as soon as possible, and within 6 hours following reconstitution and/or dilution for iv infusion. Store LEUKINE powder, reconstituted solutions, or diluted solutions under refrigeration at 2-8°C (36-46°F); do not freeze or shake. LEUKINE vials are intended for single use only; discard any unused solution after 6 hours. Do not use beyond the expiration date printed on the vial.

5.2.6 In the absence of compatibility and stability information, no other medication should be added to infusion solutions containing LEUKINE. Use only 0.9% Sodium Chloride Injection, USP to prepare iv infusion solutions.

5.2.7 Aseptic technique should be employed in the preparation of all LEUKINE Solutions. To assure correct concentration following reconstitution, care should be exercised to eliminate any air bubbles from the needle hub of the syringe used to prepare the diluent. Parenteral products should be inspected visually for particulate matter and discoloration prior to administration whenever solution and container permit.

5.3 13-cis-Retinoic Acid (NDC #0004-0155-01,0004-0169, 0004-0156-01-  
ISOTRETINOIN, ACCUTANE)

5.3.1 Source and Pharmacology: The exact mechanism of retinoic acid (RA)-induced maturation of tumor cells is not known. In NB cell lines it has been shown to down regulate *MYCN* RNA and protein expression, and such down regulation correlates with the ability of isotretinoin to induce tumor cell growth arrest. Recent studies using gene transfection directly implicate down regulation of *MYCN* expression by isotretinoin as a key event in achieving sustained arrest of NB cell proliferation. RA also appears to enhance normal hematopoietic differentiation by increasing the responsiveness of myeloid and erythroid progenitor cells to the action of myeloid colony stimulating activity and erythropoietin, respectively. Metabolism: RA is 99.9% bound in plasma (almost entirely to albumin) and has a half-life of 10-20 hours. The major metabolite is 4-oxoisotretinoin, and excretion is in the urine and feces. A single oral dose of 100mg/m^2 isotretinoin will produce peak plasma levels of 1-2mM. The mean peaktide as 3.2 hours after 80mg orally, with a terminal *t*1/2 of 10 to 20 hours. Administering 160 mg/m^2/day to children after autologous bone marrow transplantation has been shown to achieve 13-cis-RA levels of 5 to 7 micromolar.

5.3.2 Formulation and Stability: Isotretinoin, which is the 13-cis isomer of retinoic acid, will be used. This is a yellow-orange crystalline powder with a molecular weight of 300.44. Isotretinoin is sensitive to light and oxygen, and so it should not be removed from the capsule for longer than one hour prior to administration to the patient and it should be kept in subdued light as much as possible.

Amended: 02/24/15

## Memorial Sloan-Kettering Cancer Center IRB Protocol

IRB#: 09-159A(10)

5.3.3 Guidelines for Administration: PO with fat-containing food or milk to enhance absorption. Administration of the entire capsule is to be encouraged and small children can be trained to swallow them using similar sized candy.

5.3.4 Supplier: Isotretinoin is available commercially under the trade name ACCUTANE (Roche Laboratories) in 10mg, 20mg, and 40mg soft gelatin capsules. See package insert for further information.

## 6.0 CRITERIA FOR SUBJECT ELIGIBILITY

### 6.1 Subject Inclusion Criteria

- 6.1.1 Diagnosis of NB as defined by a) histopathology (confirmed by the MSKCC Department of Pathology), or b) BM metastases or MIBG-avid lesion(s) plus high urine catecholamine levels.
- 6.1.2 High-risk NB as defined by risk-related treatment guidelines and the International NB Staging System, i.e., stage 4 with (any age) or without ( $\geq 18$  months of age) *MYCN* amplification, *MYCN*-amplified stage 2 or stage 3 (any age), or *MYCN*-amplified stage 4S.
- 6.1.3 The patients are in first CR/VGPR after conventional therapy. They have no measurable MIBG-avid soft tissue tumor assessable for response.
- 6.1.4 Signed informed consent indicating awareness of the investigational nature of this program.

### 6.2 Subject Exclusion Criteria

- 6.2.1 Creatinine  $> 3.0$  mg/dL
- 6.2.2 ALT, AST and Alkaline Phosphatase  $> 5.0$  times the upper limit of normal
- 6.2.3 Bilirubin  $> 3.0$  mg/dL
- 6.2.4 Patients with grade 3 or higher toxicities (using the CTCAE v4.0) related to cardiac, neurological, pulmonary or gastrointestinal function as determined by physical exam. Patients must have normal blood pressure for age.
- 6.2.5 Progressive disease
- 6.2.6 History of allergy to mouse proteins.
- 6.2.7 Active life-threatening infection.

Amended: 02/24/15

## Memorial Sloan-Kettering Cancer Center IRB Protocol

IRB#: 09-159A(10)

6.2.8 Human anti-mouse antibody (HAMA) titer >1000 Elisa units/ml.

6.2.9 Inability to comply with protocol requirements.

## 7.0 RECRUITMENT PLAN

In each of the past 2 years, 46 patients were treated on the predecessor of this protocol. We anticipate at least maintaining this accrual rate, which will allow rapid realization of preliminary conclusions, with completion of the trial in 3-4 years. Given the favorable prior efficacy-toxicity profile with 3F8/GM-CSF, we expect that all patients will complete the trial. Patients will be offered participation in this study by their attending physician in the Department of Pediatrics, Memorial Sloan-Kettering Cancer Center. No patient will be identified by chart review or direct advertising. The attending physician will be responsible for explaining the study, obtaining written informed consent, and registering the patient on study. Patients will mainly be children and adolescents because of the nature of NB (90% of patients are <6 years old at diagnosis). Patients of both sexes and all ethnic backgrounds are eligible for this study.

## 8.0 PRETREATMENT EVALUATION

Pretreatment evaluations should be completed within 30 days of start of treatment. Refer to Table 1.

8.1 Complete history and physical examination.

8.2 Complete blood count, serum creatinine, blood urea nitrogen, serum aspartate aminotransferase, serum alanine aminotransferase, and serum total bilirubin

8.3 Echocardiogram.

8.4 Complete extent-of-disease evaluation.

8.4.1 Urine catecholamine levels - optional.

8.4.2 BM aspirates from bilateral anterior and bilateral posterior iliac crests, and biopsies from any two separate sites. The specimens are studied by:

- Standard histochemical methods for the presence of tumor cells.
- Immunocytology using a panel of monoclonal antibodies that react with antigens associated with NB (to [name] lab).

Amended: 02/24/15

## Memorial Sloan-Kettering Cancer Center IRB Protocol

IRB#: 09-159A(10)

- RT-PCR quantitation of tumor cells (to [name] lab)

8.4.3 CT or MRI of primary tumor site, plus other suspected sites of tumor.

8.4.4 Scintigraphic studies (MIBG scan or PET scan).

8.5 Biologic (blood) studies for phenotypes of leukocytes, and for DNA to do HLA and KIR typing, FcR2A and FcR3A polymorphism (to be drawn prior to treatment).

### 9.0 TREATMENT/INTERVENTION PLAN

**9.1 Schedule:** For patients consented on A(0) to A(7), 3F8 is dosed at 80 mg/m^2/day (cycles 1-2) or 20 mg/m^2/day (cycles 3 and beyond) and infused iv over 30-90 minutes. Starting with A(8), patients receive 3F8 at 20 mg/m^2/day for all cycles. To modulate pain from 3F8, patients are premedicated with analgesics (e.g., hydromorphone) and antihistamines (e.g., diphenhydramine or hydroxyzine). 3F8 is started ~1 hr after GM-CSF. GM-CSF is dosed at 250 mcg/m^2/day from day -5 to day +1 (i.e. Wednesday to Tuesday is customary), and is 500 mcg/m^2/day on days +2 to +4 (i.e. Wednesday to Friday), as in the predecessor protocols. Patients come off study if progressive disease occurs or if there is life-threatening grade 4 toxicity from 3F8.

The break from end of a cycle to start of next cycle is approximately 2-to-4 weeks through 4 cycles; subsequent breaks are ~6-8 weeks. 13-cis-retinoic acid is started after cycle 2. Road map/schema is in section 4.2.

Patients who develop HAMA which precludes timely treatments with 3F8/GM-CSF are eligible to receive low-dose maintenance regimens such as irinotecan alone temozolomide alone, irinotecan-temozolomide, or cyclophosphamide-topotecan. They can also receive anti-HAMA agents such as rituximab and cyclophosphamide. They resume treatment with 3F8/GM-CSF if HAMA becomes negative.

### 9.2 3F8/GM-CSF Treatment Schedule

#### 9.2.1 Treatment Schedule Cycles 1-2\*:

Days -5 to -1: GM-CSF 250 mcg/m^2/day, subcutaneously.

Days 0 and +1: GM-CSF 250 mcg/m^2/day, subcutaneously.

3F8 80 mg/m^2/day by iv infusion over 30-90 minutes.

Days +2 to +4: GM-CSF 500 mcg/m^2/day, subcutaneously.

Amended: 02/24/15

## Memorial Sloan-Kettering Cancer Center IRB Protocol

IRB#: 09-159A(10)

3F8 80 mg/m^2/day by iv infusion over 30-90 minutes.

\*For patients enrolled on protocol from A(0) to A(7)

### **9.2.2 Treatment Schedule Cycle 3 and onwards for patients enrolled on A(0) to A(7) and Treatment Schedule for all Cycles for patients enrolled on A(8) and onwards:**

Days -5 to -1: GM-CSF 250 mcg/m^2/day, subcutaneously.

Days 0 and +1: GM-CSF 250 mcg/m^2/day, subcutaneously.  
3F8 20 mg/m^2/day by iv infusion over 30-90 minutes.

Days +2 to +4: GM-CSF 500 mcg/m^2/day, subcutaneously.  
3F8 20 mg/m^2/day by iv infusion over 30-90 minutes.

Note: GM-CSF is not administered if the ANC is >20,000/uL. If HAMA develops, cycles are deferred until HAMA titer decreases to <1000 Elisa units/mL.

**9.3 13-cis-retinoic acid** is dosed at 160 mg/m^2/day, divided into two doses, x14 days. If a dose is missed, it can be made up at the end of the cycle. It is not taken on same days as 3F8. The treatment can be repeated after a minimum rest period of 14 days. 13-cis-retinoic acid is started after cycle 2 of 3F8/GM-CSF, but it can be started sooner if early HAMA develops. All patients take a total of 6 cycles of 13-cis-retinoic acid. Dose reductions due to expected side effects of 13-cis-retinoic acid (e.g., headaches, dry skin, etc.) are allowed.

## 10.0 EVALUATION DURING TREATMENT/INTERVENTION

**Note: If for any reason tests cannot be completed on day 0, they will be completed on day 1**

**10.1** CBC on day 0 and +3 of each cycle.

**10.2** C3 and CH50, on day 0 and +4 (i.e. Monday and Friday) of cycles 1 and 2.

**10.3** Phenotype of leukocytes, on day 0 prior to treatment and day +4 (i.e. Monday and Friday) of cycles 1 and 2.

**10.4** Serum (2-5 ml) for 3F8 levels pre 3F8 infusion on Day 0 (i.e. Monday) and post-3F8 infusion on Day 4 (i.e. Friday) for cycle 1 and 2.

**10.5** Blood for HAMA is obtained approximately every 1-2 months while on study (to [name] lab).

Amended: 02/24/15

## Memorial Sloan-Kettering Cancer Center IRB Protocol

IRB#: 09-159A(10)

**10.6** Liver and kidney function blood tests on day 0 and +4 of each cycle.

**10.7** Assessment of response is the same as in prior studies, including the predecessor 3F8/GM-CSF (IRB 03-077) protocol: BM studies (8.4.2) after cycle 2 and complete extent-of-disease evaluation (section 8.4) after cycle 4 of 3F8/GM-CSF and at least every 3 months through 2 years. BM studies are repeated in conjunction with MIBG or PET scan (section 8.4.4) through 2 years in patients with history of BM or cortical bone involvement, but are repeated ~every 6 months in other patients (e.g., patients who were stage 4 by virtue of metastases in distant lymph nodes, patients with *MYCN*-amplified stage 4S lacking BM involvement, or patients with *MYCN*-amplified stage 2 or stage 3).

**10.8** Pregnancy screen (females of child-bearing age) before starting *cis*-retinoic acid.

**10.9** Blood to study minimal residual disease (to [name] lab)

**10.10** Patients receiving 80 mg/m^2 of 3F8 will be monitored for their blood pressure for at least 2 days after 3F8 until a normal blood pressure has been assured. Not applicable starting with A(8)

Table 1. PRETREATMENT AND DURING THE STUDY EVALUATION

WHAT?	WHEN?
Complete history and physical examination.	Pretreatment evaluation
Complete blood count	1. Pretreatment evaluation 2. On day 0 (i.e. Monday) and +3 (i.e. Thursday).
Liver and kidney function blood tests	1. Pretreatment 2. On day 0 (i.e. Monday) and +4 (i.e. Friday)
Blood for studies of DNA to do HLA and KIR typing, FcR2A and FcR3A polymorphism (to [name] lab)	Pretreatment or on Cycle 1 Day 0 prior to 3F8.
Blood for studies of phenotypes of leukocytes (to [name] lab)	Day 0 (i.e. Monday) prior to treatment and Day 4 (i.e. Friday), cycles 1 and 2
Blood (2-5 ml) for 3F8 levels (to [name] lab)	1. Pre 3F8 infusion day 0 (i.e. Monday), cycles 1 and 2 2. Post 3F8 infusion day 4 (i.e. Friday), cycles 1 and 2
Blood for minimal residual disease studies (to [name] lab)	1. Drawn with post cycle 2 bone marrow studies 2. Drawn with bone marrows during first work-up (~3 months from start of study)
C3, CH50	On day 0 and +4 (i.e. Monday and Friday), cycles 1 and 2.
HAMA (Red Top Tube) (to [name] lab)	~Every 1-2 months while on study.

Amended: 02/24/15

## Memorial Sloan-Kettering Cancer Center IRB Protocol

IRB#: 09-159A(10)

Bone marrow studies (including 10ml heparinized for immunocytology and/or RT-PCR, to [name] lab)	

1. Pretreatment

2. At end of cycle 2

3. Subsequently,

• BM studies are repeated with MIBG or PET through 2 years for patients with history of BM or cortical bone involvement.

• But are repeated ~every 6 months in other patients (e.g., patients who were stage 4 by virtue of metastases in distant lymph nodes) while on study.

CT or MRI	

1. Pretreatment: of primary tumor site, plus other specific or suspected sites of tumor.

2. Followup: of primary site ~every 3 months through 1 year.

MIBG scan  or PET scan 	Pretreatment and ~every 3 months through 2 years
Echocardiogram	Pretreatment
Urine catecholamine levels (optional)	

1. Pretreatment

2. ~Every 3 months through 2 years.

Pregnancy screen (females of child-bearing age)	Before starting 13-cis-retinoic acid.
Blood pressure monitoring with 80 mg/m  of 3F8 – not applicable starting with A(8)	Measured for at least 2 days after 3F8 until normal blood pressure is assured.

**Note: If for any reason tests cannot be completed on day 0, they will be completed on day 1**

**\* Pretreatment evaluation should be completed within 30 days of treatment**

## 11.0 TOXICITIES/SIDE EFFECTS

**11.1** Toxicities are graded by the Common Toxicity Criteria (Version 3.0) developed by the National Cancer Institute (NCI) of the USA. All toxicities during cycle 1 will be recorded. After cycle 1, only toxicities  $\geq$  grade 3 will be recorded.

**11.2** 3F8: Reversible side-effects include pain, paresthesia, hypertension, hypotension, tachycardia, urticaria, fever, nausea, emesis, and rarely, diarrhea, serum sickness, hyponatremia, somnolence and posterior reversible encephalopathy syndrome (PRES). Other potential side-effects that may occur are bronchospasm, anaphylaxis, peripheral neuropathy, impaired accommodation of the eye and poor reactivity of pupils to light.

**11.2.1** The definition of unacceptable pain is the same as in the IRB 05-015 phase I 3F8 dose-escalation study, as reported71a:  $\geq 7$  doses of opioids administered within two hours. One dose of analgesic is defined as hydromorphone 0.015 mg/kg or equianalgesic dose of morphine sulfate.

**11.2.2** The definition of unacceptable hypertension is the same as in the IRB 05-015 phase I 3F8 dose-escalation study, as reported71a: hypertension necessitating medicinal intervention for  $>24$  hours.

Amended: 02/24/15

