### 14.0 BIOSTATISTICS

The objective of this phase II trial is to assess the anti-NB activity of high-dose 3F8 plus GM-CSF in patients in first CR/VGPR from high-risk NB after conventional therapy. The 3F8 dosing is four fold greater than the standard 3F8 dosage used in prior phase II studies.

In A(8), treatment was changed to use standard dose 3F8 ( $20 \text{ mg/m}^2/\text{day}$ ) for all cycles instead of high-dose 3F8 for cycles 1 and 2. Patients treated as such are evaluable for toxicity only.

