## Memorial Sloan-Kettering Cancer Center IRB Protocol

IRB#: 09-159A(10)

Therapeutic responses are logged on a central database and approximately 50% are reviewed by an independent committee. An annual report of the trial's progress is sent to the IRB. All of the procedures for Phase II studies outlined in MSKCC's policy are applicable to the current trial and will be followed by the investigators. The analysis of safety will include all patients who receive at least one dose of study medication. Adverse events, including all toxic effects of treatment, will be tabulated individually, and summarized by body system, according to dosage of study medication (single dose as well as cumulative doses of 3F8 and GM-CSF), and according to severity or toxicity grade. Laboratory data will be tabulated and summarized by descriptive statistics, as well as on the basis of MSKCC specified normal ranges.

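### Grade 1-2 toxicity is recorded in cycle 1 only (11.1), but 16.2 tabulates all toxicity by dose with no cycle limit, so low-grade rows by 3F8 dose at the event or by cumulative dose reached would reflect recording; separately, the SAE definition in 17.2.1 does not name grade 5

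*Combined protocol and SAP*

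**What the plan says.** **Recording.** Section 11.1 sets the rule: "All toxicities during cycle 1 will be recorded. After cycle 1, only toxicities" of grade 3 or higher are recorded.

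**Tabulation.** Section 16.2 includes everyone who received at least one dose in the safety analysis. It states: "Adverse events, including all toxic effects of treatment, will be tabulated individually, and summarized by body system, according to dosage of study medication". Dosage is then specified as "single dose as well as cumulative doses of 3F8 and GM-CSF", and severity or grade is a further dimension. The section neither limits these tables to cycle 1 nor refers back to 11.1. It also does not say whether dose means the dose at the event, the patient's total or the starting dose. Laboratory results are handled apart: "Laboratory data will be tabulated and summarized by descriptive statistics".

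**Dose by cycle.** Section 9.1 begins "For patients consented on A(0) to A(7), 3F8 is dosed at 80" mg/m2/day, which applies to cycles 1-2, with 20 mg/m2/day from cycle 3. From A(8) every cycle is at 20 mg/m2/day, and section 14.0 says of these patients: "Patients treated as such are evaluable for toxicity only".

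**Serious events.** Section 17.2 requires any SAE to reach the IRB/PB within 5 calendar days. Section 17.2.1 defines SAEs as grade 4 toxicities, less a list of exceptions. Neither section mentions grade 5 or death.

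**The concern.** The recording rule depends on cycle, and in this trial 3F8 dose also depends on cycle. A low-grade row at a later cycle's dose can therefore be thin or empty because nobody wrote the events down, not because they did not happen. A reader of a table by dose at the event could conclude that 80 mg/m2 causes more mild toxicity than 20 mg/m2. A reader of a table by cumulative dose reached could conclude that mild toxicity disappears with continued treatment. Neither conclusion would rest on observation.

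The safety objective in section 2.0 is to look for effects not seen in the earlier phase I study, and toxicity is the only purpose for which patients treated from A(8) are evaluable. Readers therefore need to know which rows can be compared.

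The SAE wording is a separate matter. Read literally, the most serious outcome falls outside the definition that triggers the 5-day report.

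**Working it through.** The plan states no figure of its own on this point, so there is none to reproduce. The check counts which cycles can yield a grade 1-2 clinical record.

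**Inputs.** Five 3F8 days per cycle and treatment through 24 months (4.2); 3F8 dose by cycle (9.1, 9.2); GM-CSF 250 mcg/m2 on days -5 to +1 and 500 mcg/m2 on days +2 to +4 (9.2); grade 1-2 recorded in cycle 1 only (11.1).

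**1. By 3F8 dose at the event**

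| Patients | Dose (mg/m2/day) | Cycles | Cycles with grade 1-2 recorded |
|---|---|---|---|
| A(0)-A(7) | 80 | 1-2 | 1 of 2 |
| A(0)-A(7) | 20 | 3 onward | 0 |
| A(8) onward | 20 | all K | 1 of K |

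**2. How far the size can move.** Let p be the share of patients from A(8) onward and K the cycles per patient, with equal true rates at both doses.

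- Share of cycles recorded at 80 mg/m2: 1/2. Share at 20 mg/m2: p / [(1-p)(K-2) + pK].
- Ratio of recorded rates, 80 to 20, per cycle: [K - 2 + 2p] / (2p).
- K = 2: 2p/(2p) = 1, no distortion.
- K = 6 (the cycles drawn in 4.2), p = 0.5: (4 + 1)/1 = 5. With p = 0.25: (4 + 0.5)/0.5 = 9.
- Filling 24 months with the stated breaks gives K of about 13 to 18, depending on break length and on whether the GM-CSF lead-in adds to each cycle. K = 13, p = 0.5: (11 + 1)/1 = 12. K = 18, p = 0.1: (16 + 0.2)/0.2 = 81.
- Counting patients with an event instead, where f is the share of A(0)-A(7) patients reaching cycle 3: [(1-p)f + p]/p. With p = 0.5: 2 at f = 1, and 1.5 at f = 0.5.
- Grouped by starting dose: every patient contributes one fully recorded cycle to his or her own group, so the patient-level ratio is 1.

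The values of p, K and f are assumptions; the documents report none of them. These cases run from 1 to 81, which is why no one value can stand for the effect.

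**3. By cumulative dose reached.** The scheduled total at the end of cycle 1, beyond which no grade 1-2 clinical event can appear, is:

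- 3F8, A(0)-A(7): 5 x 80 = 400 mg/m2.
- 3F8, A(8) onward: 5 x 20 = 100 mg/m2.
- GM-CSF, both: 7 x 250 + 3 x 500 = 3,250 mcg/m2 (less if withheld for a high ANC).

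For scale, six cycles would give 800 + 4 x 100 = 1,200 mg/m2 3F8 in A(0)-A(7), 6 x 100 = 600 mg/m2 from A(8), and 6 x 3,250 = 19,500 mcg/m2 GM-CSF. Grouping patients by their final total avoids empty rows. The low-grade counts would still all come from cycle 1, so a true effect of accumulating dose could not show.

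**4. What is not distorted.** Grade 3 or higher toxicity is recorded in every cycle. Laboratory values have their own tables. GM-CSF at 250 and at 500 mcg/m2 both occur in every cycle, cycle 1 included, so the recorded share is the same for both single-dose levels.

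**5. SAE wording.** Section 13.2 speaks of life-threatening grade 4 toxicity, so grade 4 does not obviously take in a fatal event. Section 11.1 would still record one, because grade 5 is above grade 3.

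**The case against.** The strongest reply is that 16.2 fixes no layout. All toxic effects may mean all that 11.1 has recorded, and since patients from A(8) are evaluable for toxicity alone, a table by cohort is as natural as one by dose at the event. On a starting-dose layout there is no imbalance. That stands: the documents leave an ambiguity and do not demonstrate a biased table. It does not settle the matter, because an A(0)-A(7) patient who reaches cycle 3 has received two single doses of 3F8 and cannot be placed in one row without a rule that 16.2 lacks.

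It is also fair that no internal test of 80 against 20 mg/m2 is planned. The safety objective looks to the earlier phase I study, and section 4.1 compares clinical results with predecessor trials. High dose is confined to cycles 1-2, and cycle 1 is fully recorded. For that objective, the gap is low-grade toxicity in cycle 2 and any late low-grade effects.

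A reader might go on to infer that every dose table must drop grades 1-2. The documents do not support that, since GM-CSF single-dose rows are recorded evenly.

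On serious events, a reader might infer that deaths would go unreported. That does not follow either. Section 17.0 commits to GCP and applicable law, 17.2 provides for forwarding IND reports to the FDA, and the institutional procedures cited in 16.2 were not supplied and may cover fatal events. None of these amends the wording of the trigger in 17.2.1, so the omission remains.

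**Conclusion.** Sections 11.1 and 16.2 do not fit together for grade 1-2 clinical toxicity. If 16.2 is carried out by 3F8 dose at the event, equal true rates would show a false excess at 80 mg/m2 whenever patients continue past cycle 2. If it is carried out by cumulative dose reached, the low-grade rows are empty after cycle 1 by rule. The conclusion is conditional on those layouts. A multiplier might be read into the illustrations above, but the layout, number of cycles and cohort share are all unfixed, so no single ratio should be quoted.

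The consequence is confined to the safety tables and how they are read. No endpoint or stopping rule uses grade 1-2 counts. Isotretinoin is a side issue, as the dose tables cover 3F8 and GM-CSF only. But "13-cis-retinoic acid is started after cycle 2 of 3F8/GM-CSF, but it can be started sooner if early HAMA develops", so its low-grade clinical effects will generally go unrecorded, while low-grade laboratory effects remain recoverable.

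The grade 5 omission holds on the text, as a gap in the SAE definition rather than in recording. Both points should be corrected.

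**What to change.** In section 16.2:

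- Limit the 3F8 single-dose tables, and the 3F8 and GM-CSF cumulative-dose tables, to grade 3 or higher.
- Show all-grade toxicity for cycle 1 only, by cycle 1 3F8 dose: 80 mg/m2 for A(0)-A(7), 20 mg/m2 from A(8). GM-CSF single-dose rows may stay all-grade within cycle 1.
- Label the cycle 1 table descriptive and confounded with enrolment period. Note that surveillance also differs, since under 10.10 only patients receiving 80 mg/m2 "will be monitored for their blood pressure for at least 2 days after 3F8 until a normal blood pressure has been assured".
- State that conclusions on clinical toxicity after cycle 1, isotretinoin included, apply to grade 3 or higher only.

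Separately, reword the SAE definition in 17.2.1 to include grade 5 toxicities.

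The table changes are analysis and reporting wording. They need no new data and alter no endpoint, sample size or recording burden. The SAE change is one line; the documents give no figure for how many additional reports it would bring.
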